6.2.2. Analysis of Secondary Endpoints

The FAS will be the primary analysis set for secondary efficacy endpoints. No formal statistical testing is planned.

Clinical improvement based on scoring using the 7-point Ordinal Scale

For each cohort and overall total, clinical status and change from Baseline in clinical status by Study Day as well as last available assessment will be summarized by the number and percentage of participants for each category. It should be noted that the main timepoint of interest for this endpoint is Day 10. In addition, a stacked bar chart will also be provided for each cohort and overall total depicting the percentage of participants for each category by Study Day. Furthermore, descriptive statistics for change from Baseline in clinical status by Study Day and last available assessment will also be provided for each cohort and overall total. Time to clinical improvement (days) will be modelled using a competing risk analysis. The competing event is death. Participants not achieving clinical improvement at the last assessment will be censored on the day of the last clinical assessment. In addition, the cumulative incidence from the competing risk analysis will also be graphically presented. The number and percentage of participants with clinical improvement will also be summarized by cohort and overall total.

Time to \geq 1-point improvement from baseline clinical status or discharged alive on the 7-point ordinal scale will be modelled using a competing risk analysis. The competing event is death. Participants not achieving \geq 1-point improvement at the last assessment will be censored on the day of the last clinical assessment. In addition, the cumulative incidence from the competing risk analysis will also be graphically presented. Furthermore, the number and percentage of participants with a \geq 1-point improvement or discharged alive based on the 7-point ordinal scale on Day 2 through Day 10 as well as last available assessment will be summarized by cohort and overall total.

Time to recovery based on the 7-point ordinal scale will be modelled using a competing risk analysis. The competing event is death. Participants not achieving recovery at the last assessment will be censored on the day of the last clinical assessment. In addition, the cumulative incidence from the competing risk analysis will also be graphically presented. Furthermore, the number and percentage of participants with recovery based on the 7-point ordinal scale on Day 2 through Day 10 as well as last available assessment will be summarized by cohort and overall total.

Clinical improvement based on scoring using the PEWS Improvement Scale

For each cohort and overall total, clinical status and change from Baseline in clinical status by Study day will be summarized for the number and percentage of participants for each PEWS improvement scale category (behavior, cardiovascular, respiratory) as well as total score. It should be noted that the main timepoint of interest for this endpoint is Day 10. A stacked bar chart will also be provided for each cohort and overall total for each PEWS improvement scale category (behavior, cardiovascular, respiratory) depicting the percentage of participants for each category by Study Day.

Time to ≥ 2 -point improvement or discharged alive will be modelled using a competing risk analysis for each PEWS improvement scale category (behavior, cardiovascular, respiratory). The competing event is death. Participants not achieving ≥ 2 -point improvement at the last assessment will be censored on the day of the last clinical assessment. In addition, the cumulative incidence from the competing risk analysis for each PEWS improvement scale category (behavior, cardiovascular, respiratory) will also be graphically presented. The number and percentage of participants with a ≥ 2 -point improvement or discharged alive on Day 2 through Day 10 or discharged alive for each PEWS improvement scale category (behavior, cardiovascular, respiratory) will also be summarized by cohort and overall total.

Time to \geq 1-point improvement or discharged alive will be modelled using a competing risk analysis for each PEWS improvement scale category (behavior, cardiovascular, respiratory). The competing event is death. Participants not achieving \geq 1-point improvement at the last assessment will be censored on the day of the last clinical assessment. In addition, the

cumulative incidence from the competing risk analysis for each PEWS improvement scale category (behavior, cardiovascular, respiratory) will also be graphically presented. Furthermore, the number and percentage of participants with $a \ge 1$ -point improvement or discharged alive on Day 2 through Day 10 or discharged alive for each PEWS improvement scale category (behavior, cardiovascular, respiratory) will be summarized by cohort and overall total.

Time to recovery based on the PEWS scale on Day 2 through Day 10, and last available assessment will be modelled using a competing risk analysis for each PEWS improvement scale category (behavior, cardiovascular, respiratory). The competing event is death. Participants not achieving a score of 0 at the last assessment will be censored on the day of the last clinical assessment. In addition, the cumulative incidence from the competing risk analysis for each PEWS improvement scale category (behavior, cardiovascular, respiratory) will also be graphically presented. Furthermore, the number and percentage of paricipants with recovery based on the PEWS scale on Day 2 through Day 10, and last available assessment for each PEWS improvement scale category (behavior, cardiovascular, respiratory) will be summarized by cohort and overall total.

Time (days) to discharge from hospital

Time to discharge from hospital will be modelled using a competing risk analysis. The competing event is death. Participants not discharged from hospital will be censored on the day of the last clinical assessment. In addition, the cumulative incidence from the competing risk analysis will also be graphically presented.

Descriptive statistics for duration of hospitalization from Day 1 and total duration of hospitalization will also be provided for each cohort and overall total. In addition, information on hospitalization status will be summarized for each cohort and overall total. Only participants who are discharged alive on or prior to Day 30 will be included in the duration of hospitalization through Day 30 follow-up visit analysis.

Oxygen usage and ventilation modality and settings

Descriptive statistics will be provided by cohort and overall total for the number of days of oxygen support through discharge alive, death or Day 10 based on the 7-point ordinal scale reported values, including:

- Days on invasive mechanical ventilation
- Days on high flow oxygen devices
- Days requiring low flow supplemental oxygen

As oxygen support status will be collected only while the participant is in the hospital, if a participant is discharged alive and dies afterwards, the participant will be included only in the summary for participants discharged alive.

Change from baseline in SARS-CoV-2 viral load up to Day 10 or up to the first confirmed negative PCR result (whichever comes first)

Descriptive statistics for viral load and change from baseline in viral load will be provided by cohort and overall total for the following:

- Day of discharge and each study day up to Day 10 or up to the first confirmed negative PCR result (whichever comes first)
- Day of discharge and each study day up to Day 10

Separate summary tables will be provided for each sample type: (a) nasal/oropharyngeal samples, (b) nasopharyngeal/oropharyngeal samples, (c) endotracheal tube (ET) aspirates, and (d) rectal or fecal swabs.

Days to the first confirmed negative PCR result, where confirmed is defined by 2 consecutive negative PCR results

For each cohort and overall total, the number and percentage of participants with:

- At least 1 negative PCR result
- Confirmed negative PCR result

will be summarized separately for each sample type: (a) nasal/oropharyngeal samples, (b) nasopharyngeal/oropharyngeal samples, (c) ET aspirates, and (d) rectal or fecal swabs.

Time to first confirmed negative PCR result will be modelled separately for each sample type: (a) nasal/oropharyngeal samples, (b) nasopharyngeal/oropharyngeal samples, (c) ET aspirates, and (d) rectal or fecal swabs, using a competing risk analysis. The competing event is death. Participants not not achieving a confirmed negative PCR at the last assessment will be censored on the day of the last clinical assessment.

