1.3. Sample Size and Power

The total sample size will be at least 52 participants.

Twelve (12) participants for each cohort (Cohorts 1-4) will be enrolled in this study. Pharmacokinetic data from these participants will provide >99% power for each cohort to conclude exposure equivalence of RDV AUC_{tau} in adolescents and children vs. 25 healthy adult participants in GS-US-399-5505 study (see Table 1-2) using two one-sided tests with each performed at an alpha level of 0.05. In this power analysis, it is assumed that the expected geometric mean ratio of AUC_{tau} between the adolescents and children group vs. the adult group is equal to 1, the inter-participant standard deviation (SD) (natural log scale) of AUC_{tau} is 0.18, and the equivalency boundary is 70% to 143%.

Meanwhile, twelve (12) participants from each cohort (Cohorts 1-4) will also provide >99% power to conclude exposure equivalence of RDV C_{max} in adolescents and children, compared to 26 healthy adult participants in GS-US-399-5505 study (see Table 1-2), assuming the expected geometric mean ratio of C_{max} between the adolescents and children group and the adult group is equal to 1, the inter-participant SD (natural log scale) of C_{max} is 0.19, and the equivalency boundary is 70% to 143%.

Sample size and power calculations were made using the software package nQuery Advisor(R) Version 8.5.

Table 1-2. Remdesivir, Nucleoside Metabolite GS-441524, and GS-704277 Plasma PK Parameters by Dose Following 30-Minute IV Infusion(s) of Remdesivir in Healthy Adult Participants in GS-US-399-5505

Study	GS-US-399-5505			
	Multiple RDV Dose (100mg)			
PK Parameter ^a		Day 5 and 10		
		$N = 26^{b}$		
Plasma RDV	Remdesivir	GS-441524 Metabolite	GS-704277 Metabolite	
C _{max} (ng/mL)	2228.8 (19.2)	145.0 (19.3)	245.5 (33.9)	
C _{tau} (ng/mL)		69.2 (18.2)		
C _{last} (ng/mL)	8.1 (46.9)	12.2 (50.0)	3.9 (27.5)	
T _{max} (h)	0.68 (0.25, 0.75)	1.51 (1.50, 2.00)	0.75 (0.75, 0.78)	
T _{last} (h)	4.00 (4.00, 4.02)	96.00 (96.00, 96.00)	8.00 (8.00, 8.00)	
t _{1/2} (h) ^d	0.96 (0.86, 1.08)	27.36 (25.29, 30.32)	1.23 (1.15, 1.38)	
AUC _{last} (h·ng/mL)	1562.8 (17.0)	4189.3 (17.7)	454.4 (31.8)	
AUC _{tau} (h·ng/mL)	1585.3 (16.6)	2229.2 (18.4)	461.5 (31.4)	
CL _{ss} (mL/h)	65068.7 (19.8)			
V _z (mL)	92557.2 (29.5)			

% CV = percentage coefficient of variation; IV = intravenous; PK = pharmacokinetic; Q1 = first quartile; Q3 = third quartile; $RDV = remdesivir (GS-5734^{TM})$

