6.2. Secondary Efficacy Endpoints

6.2.1. Definition of Secondary Efficacy Endpoints

Clinical improvement based on scoring using the 7-point Ordinal Scale

Clinical improvement improvement based on scoring using the 7-point Ordinal Scale will be derived as follows:

- If a participant dies while hospitalized (as recorded on the Death Report eCRF and Hospitalization Information eCRF), the endpoint on the day of death and all subsequent days through Day 10 will be set to Death (=1).
- If the participant is discharged alive, the endpoint on the day of discharge alive and all subsequent days through Day 10 will be set to Not hospitalized (=7).
- If the participant is discharged alive and dies on the same day or a later day (as recorded on the Death Report eCRF and Hospitalization Information eCRF), the endpoint on the day of discharge alive and all subsequent days until the day of death will be set to Not hospitalized (=7). On the day of death and all subsequent days through Day 10, the endpoint will be set to Death (=1).

Every effort will be made to obtain clinical status data for all participants prior to discharge alive. The last known clinical status will be used for days with missing clinical status (eg, where the reason for Hospital Discharge is not "Discharged Alive" and the participant has not died). All postbaseline days with missing ordinal scale score, from Day 2 to Day 10, will use the previous last known clinical status.

Clinical improvement is investigated in two settings:

- ≥ 1 point improvement from baseline clinical status or discharged alive
- \geq 2-point improvement from baseline clinical status or discharged alive on the 7-point ordinal scale

Recovery is defined as an improvement from a baseline score of 2 through 5 to a score of 6 or 7, or an improvement from a baseline score of 6 to a score of 7.

Clinical improvement based on scoring using the PEWS Improvement Scale

Clinical improvement is investigated in two settings:

- ≥ 1 point improvement from baseline clinical status or discharged alive
- \geq 2-point improvement from baseline clinical status or discharged alive on the 7-point ordinal scale

Recovery is defined as an improvement from a baseline score of 1-3 to a score of 0, or being discharged alive, whichever comes first.

Time (days) to discharge from hospital

- Duration of hospitalization from Day 1 = number of days from first dose to date discharged alive.

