- Time to ≥ 2 point improvement and time to ≥ 1 point improvement: if a participant did not experience the event of interest and did not die, the participant was censored at the last non-missing assessment date. Participants who died were considered to have experienced a competing event.
- Time to recovery: Participants not achieving recovery at the last assessment were censored on the day of the last assessment. Participants who died were considered to have experienced a competing event.
- Time to discharge from hospital: Participants not discharge at the last assessment were censored on the day of the last clinical assessment. Participants who died were considered to have experienced a competing event.

18) Details on the LOQ and LOD for the viral load samples are provided below.

Table 13-3.Viral Load Sample Details

Sample type	Limit of quantitation (copies/mL)	Limit of detection (copies/mL)
Nasal/oropharyngeal samples Nasopharyngeal/oropharyngeal samples ET aspirates	1018	925
Rectal or fecal swabs	488	306

- 19) Quantitative and categorical summary on SARS-CoV2 results and change from baseline in SARS-CoV-2 viral load up to Day 10 or up to the first confirmed negative PCR result (whichever comes first)
 - For quantitative summary (e.g., mean viral load, change from baseline etc.), "Inconclusive" SARS-CoV2 result is set to missing
 - For categorical SARS-CoV2 summary, 3 categories will be included, i.e. Positive, Inconclusive, Negative
 - Positive = Any numeric result or "< 1018cp/mL SARS-CoV-2 detected" (for Nasal/oropharyngeal samples, Nasopharyngeal/oropharyngeal samples, or ET aspirates) or "< 488cp/mL SARS-CoV-2 detected" (for rectal or fecal swabs)
 - Negative = "No SARS-CoV2 detected"
 - Inconclusive = "Inconclusive"

20) Days to the first confirmed negative PCR result

- Categorical SARS-CoV2 and SARS-CoV2 negative summary will be separated out by sample type. There will be no combined positive or negative category using 2 or 3 sample types.
- Confirmed negative PCR result is defined as 2 consecutive negative results, or negative at last available sample for participants who completed or discontinued from study. Notice 2 negative results from the same day do not equal confirmation.
- For a negative SARS-CoV2 confirmation, "Inconclusive" SARS-CoV2 result will not be considered as missing thus a "Negative" followed by a "Inconclusive" is NOT a confirmed negative PCR result.

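### The censoring rules for time to improvement conflict between SAP section 6.2.2 and Appendix 3 item 17, and neither place says that death competes only if it comes before the event

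*SAP*

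**What the plan says.** Section 6.2.2 models time to clinical improvement, time to ≥1-point improvement and time to recovery on the ordinal scale with a competing-risk analysis in which death is the competing event. For clinical improvement the censoring rule is: "Participants not achieving clinical improvement at the last assessment will be censored on the day of the last clinical assessment". The ≥1-point paragraph repeats the pattern, and for recovery the rule is: "Participants not achieving recovery at the last assessment will be censored on the day of the last clinical assessment".

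Appendix 3 item 17 restates the censoring rules for programming. For ≥2- and ≥1-point improvement it reads: "if a participant did not experience the event of interest and did not die, the participant was censored at the last non-missing assessment date". For recovery it goes back to the last assessment: "Participants not achieving recovery at the last assessment were censored on the day of the last assessment". Each of these bullets then adds: "Participants who died were considered to have experienced a competing event".

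Section 6.2.1 counts discharge alive as improvement. It scores a discharged child 7 from the day of discharge through Day 10. If the child dies later, the score is 7 until the day of death and 1 from then on.

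**The concern.** A cumulative incidence of time to improvement needs one first transition per child: the event, death without the event, or censoring. The plan states the improvement rule twice, and the two versions sort children differently. Section 6.2.2 looks at status on the last assessment. Item 17 looks at whether the event ever happened. For recovery, both places look at the last assessment, so item 17 does not clear up the wording.

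The death sentence raises a separate problem. A death can compete with improvement only if it prevents it. A child discharged alive has already improved under section 6.2.1, so a later death cannot be a competing event for that endpoint. Item 17 sets no such condition and no time limit.

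At stake is whether two programmers who follow the document would draw the same curves. The estimand is also at stake: time to first improvement and time to an improvement that lasts are different quantities.

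**Working it through.** The plan gives no figure for this point. Its only power statement concerns pharmacokinetic exposure and has no bearing here. The check is a reading of the rules, followed by an illustration of size.

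**Step 1. Classify two assumed children under each rule, read literally.** Child A meets the criterion on Day 4 and has lost it by the last assessment, alive and in hospital. Child B meets it on Day 5 and dies on Day 9.

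| Rule | Child A | Child B |
|---|---|---|
| Section 6.2.2, improvement | censored at last assessment | competing event, or censored (last status is death) |
| Item 17, ≥1- and ≥2-point improvement | event, Day 4 | competing event, Day 9 |
| Section 6.2.2, recovery | censored at last assessment | competing event, or censored |
| Item 17, recovery | censored at last assessment | competing event, Day 9 |
| Ordinary first-event rule | event, Day 4 | event, Day 5 |

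The two improvement rows conflict for A. The two recovery rows agree for A, but both depart from a first-event rule. No row taken from the plan keeps B as an event.

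**Step 2. Who can be affected.** After discharge alive the score stays at 7 through Day 10 unless the child dies. Relapse can therefore only be seen in hospital. The other route is death after improvement. If no child does either, all readings give the same curve.

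**Step 3. Size, with assumed data.** Section 1.3 gives the cohort size: "Twelve (12) participants for each cohort (Cohorts 1-4) will be enrolled in this study". It also gives a total of at least 52, which is 4 × 12 + 4. Assume a cohort of 12:

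- 8 children improve and stay improved, one on each of Days 2 to 9.
- 2 never improve and are censored on Day 10.
- The other two are A and B.

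The cumulative incidence adds, on each event day, S × d/n. S is the proportion still free of any event just before that day, d the number improving and n the number at risk.

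- First-event rule: 10 events and no earlier censoring, so 10/12 = 83.3%.
- Section 6.2.2: 7 events by Day 8 give 7/12, with S = 5/12. On Day 9, 5 are at risk and 1 improves: 7/12 + (5/12)(1/5) = 8/12 = 66.7%. The result is the same whether B is competing or censored on Day 9.
- Item 17, improvement: 8 events by Day 8 give 8/12, with S = 4/12. On Day 9, 4 are at risk and 1 improves: 8/12 + (4/12)(1/4) = 9/12 = 75.0%.

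For 52 children, add 40 more in the same pattern (32 improved and stayed improved, 8 never improved):

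- First-event rule: 42/52 = 80.8%.
- Section 6.2.2: 40/52 = 76.9%.
- Item 17, improvement: 41/52 = 78.8%.

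Per reclassified child the shift is 1/12 = 8.3 points in a cohort and 1/52 = 1.9 points overall. It is exactly this size when nobody is censored before the last event, as here. Earlier censoring would change the amount.

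**The case against.** The strongest reply is that the section 6.2.2 phrase means *by* the last assessment. A time-to-event analysis with competing risks conventionally takes the first transition. The same paragraphs already ask for separate counts at the last available assessment, and section 3.8.3 says that a time-to-event analysis does not need one value per day or window. A rule based on final status would also leave the event day undefined for a child who is improved at the end. On this view item 17 states the intent for improvement. Its death sentence merely classifies the remaining children, those who had no event and died.

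Much of this is plausible as intent, and it limits the finding. It does not remove it. Because last-assessment status is a real output in the plan, the literal reading is open to a programmer. The plan words such rules plainly elsewhere: PEWS recovery has "or being discharged alive, whichever comes first", and item 20 censors children without a confirmed negative PCR. Even if *at* means *by*, the death sentence still lacks the condition that death came before the event.

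A reader might infer more than the text supports:

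- **That the plan ignores first events throughout.** It does not. The item 17 improvement bullet censors on an ever/never basis.
- **That the two recovery rules contradict each other.** They share the last-assessment wording. The trouble there is its literal meaning.
- **That a mismatch between the curves and the by-day counts is a sign of error.** By-day counts are status on that day. They differ from a first-event curve whenever a child relapses, and would still do so after the correction.

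**Conclusion.** The point stands as a conflict of wording with a definite consequence. For ≥1- and ≥2-point improvement, section 6.2.2 and item 17 classify an in-hospital relapser differently. For recovery, both places literally censor a child who recovered and relapsed. Item 17 makes death a competing event without requiring that it precede the event, although section 6.2.1 foresees death after discharge.

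The size is about 8.3 points per affected child in a cohort of 12, and about 1.9 points among 52, on the assumption of complete follow-up to the last event. The number of affected children is not in the document. The percentages worked out above are therefore an illustration and do not predict a large shift; the shift may be zero. The outputs are descriptive secondary ones: the study has no primary efficacy endpoint and plans no formal testing. The correction is worth making because it is cheap and the cohorts are small. No conclusion on safety or pharmacokinetics depends on it.

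**What to change.** Put one rule in section 6.2.2 and in Appendix 3 item 17 for all ordinal time-to-event endpoints:

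- The event is the first postbaseline day on which the criterion is met, including discharge alive where the endpoint definition counts it. It is kept whatever follows.
- Death is a competing event only if it occurs before that day.
- Children alive who never met the criterion are censored at their last assessment.

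Apply the same rule to the PEWS endpoints in section 6.2.2, which carry the same last-assessment wording. If sustained improvement or recovery is intended, define it as a separate endpoint. Report, by cohort and overall, how many children met the event and later lost it or died.

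The cost is a few sentences and one derivation, with no new data. Section 1 requires changes made after the SAP is final to be documented in the study report, so the clarification should be recorded there.

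### The PEWS endpoints carry two wording errors, have no Day 10 rule for children discharged or dead, and do not separate score gains from discharges in children who start at the scale's floor

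*SAP*

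**What the plan says.** **Events.** In SAP Section 6.2.2, time to the ≥1-point and ≥2-point PEWS "improvement or discharged alive will be modelled using a competing risk analysis for each PEWS improvement scale category (behavior, cardiovascular, respiratory"), with death as the competing event. The matching counts by day also include discharge. Section 6.2.1 says of PEWS recovery: "Recovery is defined as an improvement from a baseline score of 1-3 to a score of 0, or being discharged alive, whichever comes first". Its PEWS bullet for the ≥2-point event names the 7-point ordinal scale as the scale of measurement.

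**Population.** "The FAS will be the primary analysis set for secondary efficacy endpoints". Section 3.1.2 requires only one dose of study drug, so no minimum baseline PEWS applies.

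**Censoring.** For the ≥2-point event, Section 6.2.2 says: "Participants not achieving ≥ 2 -point improvement at the last assessment will be censored on the day of the last clinical assessment". For recovery it says: "Participants not achieving a score of 0 at the last assessment will be censored on the day of the last clinical assessment". Appendix 3, item 17, says for the point-improvement events: "if a participant did not experience the event of interest and did not die, the participant was censored at the last non-missing assessment date". For recovery it says: "Participants not achieving recovery at the last assessment were censored on the day of the last assessment".

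**By-day display.** Status and change from baseline are tabulated by study day for each category and for the total score, and Day 10 is named as the main timepoint. On the figure, Section 6.2.2 says: "A stacked bar chart will also be provided for each cohort and overall total for each PEWS improvement scale category (behavior, cardiovascular, respiratory) depicting". The quantity plotted is the share of children at each level on each study day. Section 3.8.2 and Appendix 2 give levels 0 to 3 in each category. Section 3.6.1 leaves missing data unimputed unless a method is specified, and none is specified for PEWS.

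**The concern.** Clinical improvement on PEWS is a named secondary objective (Section 1.1), so its outputs should show what happened to the score and to whom. As written, three things get in the way.

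- One event definition points to a different scale, and the body's recovery censoring disagrees with both the definition and the appendix. Two programmers could code these endpoints differently.
- The Day 10 table and bars may be read as the cohort's status when they cover only the children still scored.
- A child who is normal in one category throughout is counted as improved in that category on leaving hospital. Because discharge is already an endpoint of its own, a reader of the PEWS event results cannot tell how much they add to it.

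**Working it through.** The SAP gives no PEWS figure to reproduce. The first two checks compare texts; the third is exact arithmetic.

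**1. Definitions and censoring side by side**

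- *≥2-point event.* Section 6.2.1 refers it to the 7-point ordinal scale, where higher is better (1 is death, 7 is not hospitalized; Appendix 3, item 16). Section 6.2.2 analyses it within each PEWS category, where lower is better. Taken literally, the Section 6.2.1 bullet would repeat the ordinal-scale event already defined above it. The companion ≥1-point bullet does not name the ordinal scale.
- *Recovery.* Compare the definition in Section 6.2.1 with the two censoring sentences:

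| Child | Definition (6.2.1) | Section 6.2.2 censoring | Appendix 3, item 17 |
|---|---|---|---|
| Baseline 1–3, discharged alive with score above 0 | Recovered, by discharge | Censored (score 0 not reached) | Not censored (recovered) |
| Baseline 0, at 0 throughout, still in hospital at last assessment | Not recovered (score route needs baseline 1–3) | Not censored (score is 0) | Censored (not recovered) |

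In the first row the Section 6.2.2 sentence contradicts the definition. In the second it leaves the child neither an event nor censored. Item 17 agrees with the definition in both rows.

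**2. Who is in the Day 10 display**

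For the ordinal scale, Section 6.2.1 sets discharge to 7 and death to 1 through Day 10 and carries the last known status over missing days. Nothing equivalent is written for PEWS. Appendix 1, note b, ends daily evaluations at discharge.

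Let *n* be the Full Analysis Set count in a cohort, *m* the number still scored at Day 10, and *x* the number of those at a given PEWS level. With no imputation and no added level, the display shows *x/m*. The share of the cohort at that level is *x/n*. The two agree only if *m = n*, that is, if nobody has been discharged, has died or is otherwise missing. The SAP does not say which denominator is meant.

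**3. Floor arithmetic**

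Inputs are the range 0 to 3 per category (Section 3.8.2), 0 as best (Appendix 2), and no baseline minimum (Section 3.1.2). From baseline *b* the largest possible score gain is *b* − 0 = *b*. A gain of at least *k* points is therefore possible only if *b* ≥ *k*.

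| Baseline | Largest gain | ≥1 point by score | ≥2 points by score |
|---|---|---|---|
| 0 | 0 | no | no |
| 1 | 1 | yes | no |
| 2 | 2 | yes | yes |
| 3 | 3 | yes | yes |

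Score improvement is possible from 3 of 4 levels for ≥1 point and from 2 of 4 for ≥2 points. A child at 0 (≥1 point), or at 0 or 1 (≥2 points), can become an event in that category only through discharge. These are counts of scale levels, not shares of children.

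**The case against.** The composite is openly declared, and composites of this kind are commonly used to accommodate patients near the best score. The ordinal scale partly shares the feature: a child at baseline 5 or 6 can meet its ≥2-point criterion only through discharge. The by-day change table is score-only, and time to discharge is analysed separately, so both components are visible in some form. All of this stands, and it is why the composite should be kept. What remains unavailable is the split within the PEWS events: two separate summaries cannot show which route came first in a given child.

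It can also be said that the display point argues from silence, since table shells may fix levels and denominators. That is fair as a limit. Still, the SAP writes the rule out for the ordinal scale and omits it for PEWS, and its stated default is no imputation.

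Three stronger readings are tempting and not supported.

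- A reader might infer that the ≥1- and ≥2-point analyses will censor children discharged without a score gain, because the Section 6.2.2 sentence names only the score. The same paragraphs define the event to include discharge, and item 17 censors only children without the event of interest, so the intended handling is fairly clear. The wording needs tidying, but no effect on the estimates should be claimed.
- A reader might infer that a large share of PEWS events will be discharges in floor-level children. The SAP gives no baseline PEWS distribution and no discharge timing, so the share cannot be stated and could be small.
- A reader might infer a general conflict over the scoring period, because Sections 1.2 and 3.8.2 tie scoring to dosing while Appendix 1 marks every day to Day 10 or discharge. The two differ only for a child still in hospital after dosing ends.

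**Conclusion.** The point holds in three limited parts.

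- The PEWS ≥2-point definition names the wrong scale, and the recovery censoring in Section 6.2.2 conflicts with the definition in Section 6.2.1 and with Appendix 3, item 17. These are plain text errors and need no assumption.
- The by-day PEWS display has no rule for children discharged or dead. That it will describe only children still scored follows from the no-imputation default, provided no shell outside the SAP says otherwise.
- Floor-level children can count as improved only by discharge, and no PEWS event output shows how many do. The arithmetic is exact; how many children it touches is unknown from the document.

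No formal testing is planned and the primary objectives are safety and pharmacokinetics. The effect is on how PEWS results are read, not on any error rate. The corrections are worth making because they change what these outputs show at low cost.

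**What to change.** 1. In Section 6.2.1, remove the reference to the 7-point ordinal scale from the PEWS ≥2-point bullet.
2. In Section 6.2.2, censor PEWS recovery on not having recovered, as Appendix 3, item 17, does. In the PEWS paragraphs of Section 6.2.2 and in item 17, state that discharge alive is part of the event.
3. Add levels for discharged alive and died to the by-day PEWS status table and stacked bars, with the Full Analysis Set as denominator.
4. Keep the composite in the Full Analysis Set. Beside it, report for each category how many events were score-first and how many discharge-first, mainly for the overall total.

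The cost is SAP wording and a little programming. No new data are needed and no planned analysis is lost. Per-cohort counts in the split will be small, with 12 children in each of Cohorts 1 to 4 and possibly as few as 4 in Cohort 5, which is why the overall column should carry it. Section 1 already provides that changes after SAP finalization are documented in the study report.
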